Although viruses are the leading cause of community-acquired pneumonia (CAP) in young children, antibiotics are prescribed for most children with CAP. Antibiotic overuse has substantial societal and individual consequences, including promotion of antimicrobial resistance, antibiotic-associated side effects and severe complications. Procalcitonin (PCT) is a biomarker that is elevated in the serum of patients with bacterial infections but is not typically elevated in patients with viral infections. A low PCT level has been shown to have a high negative predictive value for detection of children with CAP caused by typical bacteria. Similarly, PCT algorithms have decreased antibiotic use without increasing adverse events in adults and children; however, clinicians may be hesitant to use PCT, as the clinical efficacy and safety of avoiding antibiotics in outpatient children with low-risk clinical characteristics and low PCT levels has not been evaluated. The overall objective of this work is to test the hypothesis that low-risk children 12-71 months of age managed as outpatients with CAP and PCT levels < 0.25 ng/mL treated with placebo have similar clinical response to those treated with antibiotics, with fewer adverse effects, through a large-scale, multi-institutional randomized trial (RCT). Given the complexities of conducting an RCT of this nature, the overall objective of this R34 protocol is to evaluate the feasibility and finalize the methods of a future large-scale trial through a 3-site pilot feasibility trial. We will implement and establish feasibility of all study procedures by conducting a 3-site pilot trial of amoxicillin vs placebo in low-risk children with CAP and PCT levels <0.25 ng/mL. We will enroll and randomize 36 children at 3 participating sites. This pilot trial will provide necessary data to plan the large-scale definitive trial, including assessment of facilitators and barriers of study participation, estimating enrollment and attrition rates, evaluating study procedures and interventions in a real-world setting, and determining adherence rates. In addition, we will demonstrate the ability to collect outcomes important to the future RCT, including clinical response, symptom resolution, adverse events and quality of life. The subsequent large RCT will be significant, as it will definitively address whether antibiotics are beneficial in low-risk children with CAP, representing an innovative departure from the status quo by shifting from empirical antibiotic use for all children with CAP to a targeted approach.

1 Study Summary

This pilot study will evaluate study processes and feasibility of a future large-scale clinical trial that proposes to test whether low-risk children managed as outpatients with community-acquired pneumonia (CAP) and procalcitonin (PCT) levels <0.25 ng/mL treated with placebo (i.e., no antibiotics) have a similar clinical response, with fewer adverse effects, compared with those treated with antibiotics.

1.1 Hypotheses

[figure not shown]
The hypothesis of this pilot study is that we will enroll and randomize at least 2 children per site per month and successfully conduct all study procedures, demonstrating the feasibility of conducting a subsequent large-scale clinical efficacy trial of antibiotics vs. placebo in low-risk children with CAP.

[figure not shown]

Pilot trials are designed with procedures similar to full-scale trials but with smaller patient enrollment to assess the feasibility and fill important knowledge gaps to inform a subsequent large-scale definitive trial. The overall objective of this pilot trial is to evaluate and finalize all trial procedures and study outcomes necessary for the development of a subsequent phase III trial evaluating antibiotics vs. placebo in low-risk children with CAP and PCT levels <0.25 ng/mL, while assessing the feasibility of study design and procedures. Knowledge gained from these pilot studies will also inform future trials of children with CAP. To achieve this overall objective, we will pursue the following specific aim:

Specific Aim 1: To demonstrate the feasibility to efficiently and effectively enroll low-risk children with CAP and PCT levels <0.25 into a multicenter RCT evaluating antibiotics vs. placebo, while refining study procedures for the subsequent large-scale clinical trial.

2 Background

3 Participant Eligibility, Accrual and Study Duration

3.1 Eligibility criteria.

Eligible participants will be identified by study staff. Inclusion criteria are:

- 1. Age 12–71 months; and
- 2. Diagnosis of CAP, defined using established criteria:
 - (a) Signs and symptoms of lower respiratory tract infection (LRTI), defined as one or more of the following:
 - · new or different cough; or
 - · new or different sputum production; or
 - · chest pain; or
 - · dyspnea/shortness of breath; or
 - · documented tachypnea; or
 - · abnormal findings consistent with LRTI on physical examination (e.g., crack-les/rales, rhonchi, wheezing) and
 - (b) Fever, defined as temperature ≥38°C, and
 - (c) ED clinician diagnosis of CAP, including intention to treat with antibiotics, and
 - (d) Chest radiography suspicious for CAP.⁴
- 3. Intention to treat as an outpatient after ED visit.

Exclusion criteria are:

- 1. Hospitalization within one month preceding study visit; or
- 2. Sustained oxygen saturations <90% with appropriate waveform on oximeter; or
- 3. Incomplete immunization status (<2 doses of Hib and pneumococcal vaccines); or
- 4. Chronic complex medical conditions (chronic heart disease, chronic lung disease (not including asthma), congenital airway or lung malformations, cystic fibrosis, chronic renal disease, protein-losing enteropathy, genetic syndromes, neurocognitive deficits, or metabolic disorders); or
- 5. Conditions that compromise the immune system (HIV, primary immunodeficiency, asplenia, sickle cell disease, receipt of hematopoietic stem cell or solid organ transplant, immunosuppressive agents, daily corticosteroids for more than 7 consecutive days in past 14 days); or
- 6. Systemic antibiotic receipt within the previous two weeks of CAP diagnosis; or
- 7. Radiographic findings of complicated pneumonia (moderate-to-large pleural effusion, empyema, abscess, necrotic lung disease); or
- 8. Pneumonia known to be due to bacterial source at the time of enrollment, as documented by blood culture or PCR if available, or another clear source of bacterial infection requiring immediate antibiotics; or

- 9. Toxic clinical appearance, sepsis, or critical illness as determined by clinical team at ED presentation; or
- 10. Diagnosed with pneumonia in the previous three months; or
- 11. Provider diagnosis of bronchitis, or aspiration pneumonia; or
- 12. Severe drug allergy to amoxicillin; or
- 13. Any other condition that in the judgement of investigators or the clinical team could affect safety of the subject; or
- 14. No access to a telephone or video technology for follow-up; or
- 15. Current enrollment in another clinical trial of an investigational agent; or
- 16. Previous enrollment in this trial; or
- 17. Parent/guardian non-English or non-Spanish speaking; or
- 18. Known allergy to milk and/or red dye.

Note: To be eligible for stage 2 randomization, the subject must have a PCT level<0.25ng/mL.

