5.1 Screening and Enrollment

Clinical research coordinators (CRCs) at participating EDs will screen potentially eligible patients with respiratory tract symptoms and discuss eligibility with the treating attending physician. If thought to be eligible and a diagnosis of CAP is presumed by the treating physician, the CRC will approach the patient to complete screening procedures. As outlined in the Trial Flow Diagram figure 1 on page 15. The informed consent process will consist of two stages.

· Stage 1: Baseline Characteristics and Serum Procalcitonin Levels

Informed consent will be obtained for the initial data collection and PCT in eligible patients. Potential participants will be informed that if eligibility criteria are met during the first phase, they will be approached to further discuss the randomized trial. The RCT will be introduced during stage 1 and participants will not be enrolled in stage 1 unless they express an interest to participate in stage 2 (the RCT).

Participants consenting during stage 1 will have the following procedures performed:

- 1. baseline characteristics, including severity factors, will be ascertained,
- 2. blood will be collected for real-time PCT testing, and
- data collected from the electronic health record (EHR) will be retained for additional observational studies.

If PCT concentration is ≥0.25 ng/mL, participation will end and no further trial procedures will occur. If the PCT is <0.25 ng/mL then the participant will proceed to the randomized trial (stage 2).

· Stage 2: Randomized Trial of Amoxicillin vs. Placebo with PCT < 0.25 ng/mL

If PCT concentration is <0.25 ng/mL, stage 2 of informed consent, with procedures specific to the RCT, will be obtained. As part of enrollment, a standardized letter will be given to families and shared with primary care pediatricians, when feasible, explaining the study, including its rationale, and any emergency contacts and procedures if clinical deterioration should occur.

Participants consenting to the following study procedures during stage 2:

- randomization to receive either oral amoxicillin or placebo for a standard course (7 days),
- 2. daily symptom diary during days 1-7 and,
- 3. a nasal swab collection in the ED at the time of the study visit, and one home collection between days 7–25 after the study visit and,
- 4. telephone or video-based follow-up at 7 and 21 days following randomization.

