5.1.1 Procalcitonin

We will employ the B·R·A·H·M·S PCT assay for this trial. This assay requires <0.5 mL of blood with a turnaround time of 30-60 minutes. As such, 0.5-1 mL of whole blood will be collected from the patient.

Protocol 047 ([name]) Page 15 of 42

[figure not shown]

Figure 1: Trial Flow Diagram

n this trial, the PCT concentration will not be revealed to the participants or any member of the clinical care team unless it is <0.25 ng/mL to allow for randomization. The PCT assay will be performed using the validated assay used for clinical care at each site.

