5.2 Randomization

After enrollment and confirmation of a PCT less than 0.25 ng/mL, patients will be randomized to a 7-day course of either amoxicillin (80-100 mg/kg divided BID up to 4,000 mg/day) or placebo. Randomization to amoxicillin or placebo will be at a 1:1 ratio with block sizes of 2 and 4. Patients will be stratified by clinical site and randomization will be performed through an online system.

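### Exclusion 6 ends its antibiotic look-back at CAP diagnosis, so a child given an antibiotic in the ED between diagnosis and randomisation could still be randomised

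*Protocol*

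**What the plan says.** Exclusion 6 in Protocol 3.1 bars "Systemic antibiotic receipt within the previous two weeks of CAP diagnosis". The window closes at diagnosis.

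Inclusion 2(c) in the same list reads "ED clinician diagnosis of CAP, including intention to treat with antibiotics, and" (the list then continues). Protocol 5.1 puts recruitment after that judgement: "If thought to be eligible and a diagnosis of CAP is presumed by the treating physician, the CRC will approach the patient". Stage 1 consent and blood sampling follow. On timing, Protocol 5.1.1 says "This assay requires <0.5 mL of blood with a turnaround time of 30-60 minutes". Stage 2 consent is taken once the result is known, and Protocol 5.2 says "After enrollment and confirmation of a PCT less than 0.25 ng/mL, patients will be randomized to a 7-day course".

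The only condition added for the second stage is the note closing Protocol 3.1: "To be eligible for stage 2 randomization, the subject must have a PCT level<0.25ng/mL". SAP 4.1 refers eligibility back to the protocol.

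The comparison of interest appears in Protocol 1, which describes children in the future large trial as "treated with placebo (i.e., no antibiotics) have a similar clinical response" to those given antibiotics.

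**The concern.** The interval between diagnosis and randomisation lies outside the antibiotic exclusion, and during it the treating clinician already has antibiotics in mind. A site applying exclusion 6 literally would have no stated reason to decline a child who had an ED dose while consent or the PCT result was pending.

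Two things are at stake, and both mainly concern the definitive trial:

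- **The contrast.** A dose given before allocation can occur in either arm. Exposure shared by both arms would tend to make them look alike on clinical response and on antibiotic side effects. That matters for a trial whose hypothesis is a similar response with fewer adverse effects, because some of the similarity could come from the shared exposure.
- **The planning rate.** The enrolment rate counts everyone randomised (SAP 4.2.9 and 5.5.1). If the definitive trial requires children with no antibiotic before randomisation, the pilot rate will include some it could not use, and their number will not be known.

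**Working it through.** **1. Order of events, from Protocol 3.1, 5.1, 5.1.1 and 5.2.** Presumed CAP diagnosis with intent to treat; coordinator approach; Stage 1 consent; blood draw; assay of 30-60 minutes; Stage 2 consent; randomisation. The look-back covers the time before the first step only. The uncovered interval is at least the assay time plus two consents.

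**2. Does anything else visible close the interval?**

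- Exclusion 8 covers pneumonia with a known bacterial source, or "another clear source of bacterial infection requiring immediate antibiotics". A dose for the CAP itself is neither. Its first limb is anchored at enrolment, so the list does use a later anchor elsewhere.
- Exclusion 13 is a judgement about the child's safety, not a rule on prior antibiotics.
- The Stage 2 condition is the PCT threshold alone.
- Baseline history (Protocol 5.5.1) is taken in Stage 1, so it could miss a dose given while the assay is running. The health-record data (Protocol 5.1) and the chart review after day 21 (SAP 3.1) might contain such a dose, but neither is said to extract it, and neither excludes the child.

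**3. The plan's own figures (SAP 8).** 3 sites × 6 months × 2 per site-month = 36 randomised. Stage 1 need: 2 / 0.40 = 5 per site-month, and 36 / 0.40 = 90 in total. Both reproduce exactly, and the wording of exclusion 6 does not alter them. With 1:1 allocation, 18 children are expected on placebo.

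**4. Possible size.** Let f be the share of otherwise randomisable children dosed between diagnosis and randomisation. The documents give no value, so f = 5%, 10% and 20% is assumed for illustration.

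| Quantity | Formula | f = 5% | f = 10% | f = 20% |
|---|---|---|---|---|
| Pre-dosed among 36 randomised | 36f | 1.8 | 3.6 | 7.2 |
| Pre-dosed among 18 on placebo | 18f | 0.9 | 1.8 | 3.6 |
| Chance of at least one on placebo | 1 − (1 − f)^18 | 60% | 85% | 98% |
| Rate per site-month if excluded | 2.0(1 − f) | 1.9 | 1.8 | 1.6 |
| Randomised from 90 in Stage 1 if excluded | 36(1 − f) | 34.2 | 32.4 | 28.8 |
| Stage 1 children needed for 36 | 90/(1 − f), rounded up | 95 | 100 | 113 |
| Months to reach 36 at the planned Stage 1 pace | 6/(1 − f) | 6.3 | 6.7 | 7.5 |

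The 2.0 is the planning target, not an observed rate. For scale, an exact Poisson 95% interval for 36 children in 18 site-months runs from 1.4 to 2.8 (the method is assumed; the SAP does not name one). The whole shift from 2.0 to 1.6 lies inside it.

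**The case against.** The strongest reply is that the written rule permits this but nothing shows that it happens. Inclusion 2(c) speaks of an intention, which suggests that treatment has not begun. The coordinator discusses eligibility with the attending before the approach, and families enter Stage 1 only if interested in the randomised trial. The attending therefore knows that the child may be allocated to amoxicillin or placebo, which makes a dose during the assay wait less likely. The Trial Flow Diagram is not shown, and the manual of operations and CRFs are not supplied; any of them might contain a check. The pilot also plans a clinician survey to refine the eligibility criteria (Protocol 6.2).

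All of this stands as a limit on how often the gap would matter. None of it closes the gap in the written criterion.

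Three stronger readings are tempting, and the documents do not support them:

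- **That exclusion 6 contradicts Protocol 1.** The phrase there glosses placebo in the comparison that the future trial proposes to test. It does not say that pilot children have had no earlier dose. This is a gap between a criterion and an aim, not two statements that cannot both be true.
- **That the pilot's results are biased.** The primary outcome is the enrolment rate of randomised children, which is correct as defined, and Protocol 6.2 rules out inference between arms. Doses before allocation are also expected equally in both arms.
- **That the pilot rate is overstated.** It would overstate supply only if the definitive trial adopted a stricter criterion, which neither document says. A single dose set against a 7-day course may also leave much of the contrast intact; the documents give no basis for quantifying the loss.

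**Conclusion.** The point holds as a gap in eligibility wording. Exclusion 6 stops at diagnosis, randomisation is later, and a child dosed in the ED in between could be randomised without breaching any visible criterion or being captured by any named data item.

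Its weight for this pilot is modest: it touches the descriptive summaries by arm and leaves the primary outcome as defined intact. Its weight is greater for the definitive trial, because the pilot exists to settle procedures for that trial. Under the assumed 5-20%, about 2 to 7 of 36 children would be affected, about 1 to 4 of them on placebo. The conclusion about the wording does not depend on that range, but every figure for its size does. It would fall away if the flow diagram, manual or CRFs turned out to contain a check up to randomisation.

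**What to change.** 1. Reconcile exclusion 6 with the intended placebo comparison by running the look-back from two weeks before CAP diagnosis up to Stage 2 randomisation, and have it confirmed when the PCT result returns. This decides who is randomised and leaves treatment decisions with the clinicians.
2. Whatever is decided on the first step, add one baseline item for any systemic antibiotic given between ED arrival and randomisation, and report the count by arm. For children who reach Stage 2 but are then excluded on this ground, report the number in the study flow. This would supply the frequency that the documents lack.
3. If the manual or CRFs already contain such a check, bring it into Protocol 3.1 so that the criterion and the practice agree.

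The cost is one clause, one data field and a brief recheck. A few Stage 1 children who have already had blood drawn become ineligible, and the enrolment rate may be somewhat lower: at the top of the assumed range, a fifth lower. If the investigators prefer to keep the present anchor, the second step alone still lets the definitive trial be planned with the exposure known.

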3.2 Participant Accrual and Study Duration

This trial will enroll over a 6-month period and take place at 3 sites that are or were sites in the Pediatric Emergency Care Applied Research Network (PECARN), a federally funded network of 18 pediatric EDs that have an established and successful history of completing large-scale clinical trials in the ED. The randomized trial (stage 2) will enroll 36 patients in total (2 patients per month, per site).

4 Study Design

This pilot clinical trial is a 3-site, randomized, placebo-controlled, double-blinded trial assessing the feasibility of comparing amoxicillin to placebo in children 12 months to <6 years of age who present to the ED with CAP, a PCT<0.25 ng/mL, and who will be treated as outpatients.

5 Study Procedures

5.1 Screening and Enrollment

Clinical research coordinators (CRCs) at participating EDs will screen potentially eligible patients with respiratory tract symptoms and discuss eligibility with the treating attending physician. If thought to be eligible and a diagnosis of CAP is presumed by the treating physician, the CRC will approach the patient to complete screening procedures. As outlined in the Trial Flow Diagram figure 1 on page 15. The informed consent process will consist of two stages.

· Stage 1: Baseline Characteristics and Serum Procalcitonin Levels

Informed consent will be obtained for the initial data collection and PCT in eligible patients. Potential participants will be informed that if eligibility criteria are met during the first phase, they will be approached to further discuss the randomized trial. The RCT will be introduced during stage 1 and participants will not be enrolled in stage 1 unless they express an interest to participate in stage 2 (the RCT).

Participants consenting during stage 1 will have the following procedures performed:

- 1. baseline characteristics, including severity factors, will be ascertained,
- 2. blood will be collected for real-time PCT testing, and
- data collected from the electronic health record (EHR) will be retained for additional observational studies.

If PCT concentration is ≥0.25 ng/mL, participation will end and no further trial procedures will occur. If the PCT is <0.25 ng/mL then the participant will proceed to the randomized trial (stage 2).

· Stage 2: Randomized Trial of Amoxicillin vs. Placebo with PCT < 0.25 ng/mL

If PCT concentration is <0.25 ng/mL, stage 2 of informed consent, with procedures specific to the RCT, will be obtained. As part of enrollment, a standardized letter will be given to families and shared with primary care pediatricians, when feasible, explaining the study, including its rationale, and any emergency contacts and procedures if clinical deterioration should occur.

Participants consenting to the following study procedures during stage 2:

- randomization to receive either oral amoxicillin or placebo for a standard course (7 days),
- 2. daily symptom diary during days 1-7 and,
- 3. a nasal swab collection in the ED at the time of the study visit, and one home collection between days 7–25 after the study visit and,
- 4. telephone or video-based follow-up at 7 and 21 days following randomization.

The DCC will prepare enrollment reports to monitor the screening and enrollment at each site to assess site performance and, if necessary, take corrective action.

5.1.1 Procalcitonin

We will employ the B·R·A·H·M·S PCT assay for this trial. This assay requires <0.5 mL of blood with a turnaround time of 30-60 minutes. As such, 0.5-1 mL of whole blood will be collected from the patient.

Protocol 047 ([name]) Page 15 of 42

[figure not shown]

Figure 1: Trial Flow Diagram

n this trial, the PCT concentration will not be revealed to the participants or any member of the clinical care team unless it is <0.25 ng/mL to allow for randomization. The PCT assay will be performed using the validated assay used for clinical care at each site.

5.2 Randomization

After enrollment and confirmation of a PCT less than 0.25 ng/mL, patients will be randomized to a 7-day course of either amoxicillin (80-100 mg/kg divided BID up to 4,000 mg/day) or placebo. Randomization to amoxicillin or placebo will be at a 1:1 ratio with block sizes of 2 and 4. Patients will be stratified by clinical site and randomization will be performed through an online system.

5.2.1 Blinding

As a double-blind clinical trial, the study patients and their parents/guardians, investigators and study staff will be blinded to study treatment assignment for the duration of the study. At the data coordinating center, only the study biostatisticians and the DSMB will be unblinded, as necessary, to treatment assignment.

